6.2.2 Guidelines for dose escalation and determination of (MTD/ RDE)

For the purposes of dose escalation decisions, 3 to 6 patients will be enrolled in successive cohorts. The first cohort will be treated with the starting dose of 280 mg/m²/d. Patients must complete a minimum of 1 cycle of treatment with the minimum safety evaluation and drug exposure or have had a DLT within the first cycle of treatment to be considered evaluable for dose escalation decisions. Dose escalation decisions will occur when the cohort of patients has met these criteria. Dose escalation decisions will be made by Investigators and Novartis study personnel. Decisions will be based on a synthesis of all relevant data available from all dose levels evaluated in the ongoing study including safety information, DLTs, all CTCAE grade \geq 2 toxicity data during Cycle 1, and PK, data from evaluable patients. PK data from patients will be made available on an on-going basis throughout the study and dosing will be adapted accordingly. The recommended dose for the next cohort of patients will be guided by the BLRM with EWOC principle.

The adaptive Bayesian methodology provides an estimate of all dose levels of LEE011 that do not exceed the MTD and incorporates all DLT information at all dose levels for this estimation. In general, the next dose will have the highest chance that the DLT rate will fall in the target interval (16-33%) and will always satisfy the EWOC principle. In all cases, the dose for the next cohort will not exceed a 100% increase from the previous dose. Smaller increases in dose may be recommended by the Investigators and Sponsor upon consideration of all of the available clinical data.

[figure not shown]
If the first 2 patients in a previously untested dose level experience a DLT, the next cohort will be opened at the next lower dose level or an intermediate dose level (see [Table 6-1](#), [Appendix 7](#)). However, if the first 2 patients in a new cohort at a previously tested dose level experience a DLT, further enrollment to that cohort will stop and the BLRM will be updated with this new information. Re-evaluation of the available safety, PK, and PD data will occur.

By incorporating information gained at the preceding dose cohorts, additional patients may be enrolled into this dose cohort only if the dose level still meets the overdose criteria and as agreed by Investigators and Novartis personnel. Alternatively, if recruitment to the same cohort may not resume, a new cohort of patients may be recruited to a lower dose as agreed by Investigators and Novartis personnel and if the BLRM predicts that the risk for this lower dose to exceed the MTD remains below 25% (EWOC).

Dose escalation will continue until identification of the MTD or a suitable lower dose for expansion. This will occur when the following conditions are met:

1. at least 6 patients have been treated at this dose
2. this dose satisfies one of the following conditions:
 - a. the posterior probability of targeted toxicity at this dose exceeds 50% and is the highest among potential doses, or
 - b. minimum of 12 patients have already been treated on the trial.
3. it is the dose recommended for patients, either per the model or by review of all clinical data by Novartis and Investigators in a dose-escalation teleconference, see [Section 6.2.2.1](#).

To better understand the safety, tolerability and PK of LEE011 additional cohorts of patients may be enrolled at preceding dose levels, or to intermediate dose levels before or while proceeding with further dose escalation.

If a decision is made to escalate to a higher dose level but one or more additional patient(s) treated at the preceding dose level experiences a DLT during the first cycle of treatment, then the BLRM will be updated with this new information before any additional patients are enrolled at that higher dose level. Patients ongoing will continue treatment at their assigned dose levels.

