Study drug discontinuation	Point/time when patient permanently stops taking study drug for any reason; may or may not also be the point/time of premature patient withdrawal
Treatment group	A treatment group defines the dose and regimen or the combination, and may consist of 1 or more cohorts. Cohorts are not expanded, new cohorts are enrolled.
Variable	Identifier used in the data analysis; derived directly or indirectly from data collected using specified assessments at specified timepoints

Amendment 2

Amendment rationale

The primary purpose of this amendment is to add language that describes the option for patients to discontinue treatment in CLEE011X2102 and transfer to a Novartis LEE011 rollover protocol which will continue to provide LEE011.

In addition, for consistency across clinical trials within the LEE011 programs, language has also been updated within the following sections:

- Definition of highly effective contraception method
- Permitted concomitant therapy
- Dosing administration

Changes to Protocol

Sections 4.3, 6.1.3, and 7.1.3 have been updated to include language regarding transfer to the LEE011 rollover protocol.

Section 5.3 Exclusion criterion bullet 16 definition of highly effective contraception method has been updated to align with new internal guidelines.

[figure not shown]
Section 6.1.2 LEE011 administration was updated to allow administration with food and to include additional citrus fruit to avoid to align with new internal program language.

Section 6.4.1.1 Corticosteroid section was added to include restrictions for corticosteroid use to align with new internal program language. Tables 7-4 and 7-5 sample numbers and PK collection numbers were removed to align with internal guidelines.

IRB/IEC/REB Approval

A copy of this amended protocol will be sent to the Institutional Review Board (IRBs)/Independent Ethics Committee (IECs) and Health Authorities.

The changes described in this amended protocol require IRB/IEC approval prior to implementation. In addition, the changes herein affect the Informed Consent and sites are required to update and submit for approval a revised Informed Consent that takes into account the changes described in this amended protocol.

Summary of previous amendment(s)

Amendment 1

18 July 2013

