6.2 Dose escalation guidelines

6.2.1 Starting dose for the dose escalation part

The first cohort of patients in this trial will be treated with a dose of 280 mg/m²/d, which is 80% of the current well tolerated dose (600 mg/d) in the ongoing adult study [CLEE011X2101] divided by the average adult body surface area (BSA) of 1.72 m². Table 6-1 describes the starting dose and the dose levels that may be evaluated during this trial.

Table 6-1 Provisional dose levels

Dose level	Proposed daily dose*	Increment from previous dose	Corresponding adult dose level
-1 [°]	210 mg/m ²	-25%	360 mg/d
1 (starting dose)	280 mg/m ²	(starting dose)	480 mg/d
2	420 mg/m ²	50%	720 mg/d
3	630 mg/m ²	50%	1080 mg/d

This table is intended only as a guide. Values in table are examples and actual doses may vary.

* Additional dose levels may be added during the course of the study. Cohorts may be expanded at any dose level below MTD in order to better understand safety, PK or PD.

[°] Dose level -1 is a dose level that may be evaluated if the starting dose level is not well tolerated

Since the adult MTD has not been established, LEE011 doses higher than 630 mg/m² may be evaluated depending on the data from the adult Ph1 study and observed safety, PK and PD.

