6.2.3 Definitions of DLTs

A DLT is defined as an AE or clinically significant abnormal laboratory value assessed as unrelated to disease, disease progression, inter-current illness, or concomitant medications that occurs within the first 28 days of treatment with LEE011 and meets any of the criteria included in [Table 6-2](#). NCI CTCAE version 4.03 will be used for all grading. For the purpose of dose-escalation decisions, DLTs will be considered and included in the BLRM.

The investigator must notify the Sponsor immediately of any unexpected CTCAE grade ≥ 3 AEs or laboratory abnormalities. Prior to enrolling patients into a higher dose level, CTCAE grade ≥ 2 AEs will be reviewed for all patients at the current dose level.

[figure not shown]

Table 6-2 Criteria for defining dose-limiting toxicities

TOXICITY	DLT CRITERIA
Hematology	CTCAE grade 4 neutropenia lasting more than 7 consecutive days
	CTCAE grade 4 thrombocytopenia
	CTCAE grade 3 or 4 neutropenia with fever (temperature $\geq 38.5^{\circ}\text{C}$)
ECG QT Interval	QTc interval ≥ 501 ms on at least two separate ECGs
Gastro-intestinal	\geq CTCAE grade 3 nausea or vomiting despite optimal anti-emetic therapy \geq CTCAE grade 3 diarrhea despite optimal anti-diarrhea treatment
Hepato-biliary	\geq CTCAE grade 3 total bilirubin \geq CTCAE grade 3 ALT (isolated increases in AST without concomitant increases in ALT will not be considered dose-limiting, because of the non-specific nature of AST)
Non-hematologic events	\geq CTCAE grade 3, except for the exclusions noted below
Exceptions to DLT criteria	Grade 3 alopecia
	< 72 hours of CTCAE grade 3 fatigue
	Grade 3 fever or infection without neutropenia < 5 days duration
	Grade 3 laboratory abnormalities that are responsive to oral supplementation or deemed by the investigator to be clinically insignificant
CTCAE version 4.03 will be used for all grading. Optimal therapy for vomiting or diarrhea will be based in institutional guidelines, with consideration of the prohibited medications listed in this protocol.	

[figure not shown]

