6.3 Dose modifications

6.3.1 Dose modification and dose delay

If a patient experiences a DLT, then treatment with LEE011 must be interrupted. For all toxicity grades, if the toxicity resolves to grade 1 or baseline within 1 week of onset, treatment may be resumed at the same or a lower dose level at the investigator's discretion and following discussion with Novartis. For toxicities that result in treatment delays of more than 7 but not more than 21 days, treatment may be resumed at a lower dose level. If a patient requires a dose interruption of > 21 days from the intended day of the next scheduled dose, then the patient must be discontinued from the study. In this event, more frequent follow up as outlined in cycle 1 to monitor this toxicity may be appropriate. Changes to the dose or schedule must be recorded on the Dosage Administration Record eCRF. All patients will be followed for AEs and for SAEs for 30 days following the last dose of LEE011.

Patients who have dose-limiting neutropenia with no other dose-limiting toxicity may receive the same dose in the next cycle with myeloid growth factor support or receive study drug at the next lower dose level. If dose-limiting neutropenia recurs after myeloid growth factor support is added, then the patient should be given the next lowest dose level for subsequent cycles and myeloid growth factor support should be administered.

Patients with extensive involvement of bone marrow who are not evaluable for hematologic toxicity but who have dose-limiting neutropenia should receive the same dose in the next cycle with myeloid growth factor support or receive study drug at the next lower dose level. Since these patients are permitted to have platelet transfusions to meet platelet criteria, no dose modifications will be made for dose-limiting thrombocytopenia.

If a patient experiences an adverse event that is considered to be related to LEE011 that requires interruption of treatment with LEE011, the following must be met in order to resume treatment with LEE011 (except for patients with bone marrow disease):

- ANC must be $\geq 1,000$ / μ l
- Platelet count must be $\geq 75,000$ / μ l
- All non-hematologic toxicities must be \leq grade 1 or returned to baseline
- Absence of any other DLTs, as described in [Table 6-2](#).

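### In an escalation cohort of more than 3 patients at an untested dose, 2 DLTs among the first 3 require no enrolment pause or model run if the second falls at patient 3

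*Protocol*

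**What the plan says.** Protocol 6.2.2 and 10.8 set escalation cohorts at 3 to 6 patients. Section 6.2.2 has two triggers that act on a cohort's own DLTs before it is complete:

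- Untested dose: "If the first 2 patients in a previously untested dose level experience a DLT", the next cohort opens at a lower or intermediate dose.
- Previously tested dose: "if the first 2 patients in a new cohort at a previously tested dose level experience a DLT, further enrollment to that cohort will stop"; a model update follows. After that stop, "additional patients may be enrolled into this dose cohort only if the dose level still meets the overdose criteria".

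Otherwise dose decisions wait until the cohort is evaluable (6.2.2), and the model is run after each cohort (Protocol 10.4.2 and 10.7; SAP 5.4.1). One further unscheduled update is written, for a late DLT at the preceding dose: "then the BLRM will be updated with this new information before any additional patients are enrolled at that higher dose level".

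The overdose criterion in 10.4.2 rules a dose out for the next cohort if the probability that its DLT rate exceeds 0.333, P(over), is above 25%. Below Table 14-15, Appendix 7 says the model reduces the dose after more than 1 DLT in 3 patients or more than 2 in 6.

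At patient level, "If a patient experiences a DLT, then treatment with LEE011 must be interrupted" (6.3.1). On reporting, "The investigator must notify the Sponsor immediately of any unexpected CTCAE grade" 3 or higher event (6.2.3), and 8.2.2 requires every SAE to reach the sponsor within 24 hours.

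**The concern.** Take a cohort that will enrol six at an untested dose, with DLTs in patients 1 and 3. Had the cohort closed at three, the model would run and the dose would come down. Because it is still open, the text lets patients 4 to 6 enter at the same dose without a model run. The same 2/3 data lead to different actions depending on planned cohort size and on which patients had the DLTs.

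Up to three more children could be dosed at a level that the plan would not offer to a new cohort. The tool needed is already in 6.2.2: a model update before more patients enter is required for a late DLT one dose level down.

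**Working it through.** **1. What the plan does with 2/3 (Table 14-15).**

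| Scenario | Data | Next dose | P(over) at next dose |
|---|---|---|---|
| 3 | 2/3 at 280 | 85 | 25% |
| 6 | 0/3 at 280, 2/3 at 420 | 280 | 15.4% |
| 13 | 0/3 at 280, 0/3 at 420, 2/3 at 630 | 420 | 10.1% |

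All three step down.

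**2. P(over) at the dose being filled.** At 280 it follows from print. The model is logit π(d) = log α + β log(d/580) with β > 0, so P(over) rises with dose. After 2/3 at 280 it is already 25% at 85 mg/m², so it exceeds 25% at 280.

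At 420 and 630 the table prints P(over) only for the lower dose chosen next. The prior is redacted, so I back-fitted bivariate priors on (log α, log β) to the 48 printed figures. This is an assumption. The fits were:

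- Single normal: mean (−1.26, −0.94), SD (0.95, 1.06), correlation 0.31; worst miss 4.3 points.
- A second single-normal fit: mean (−1.25, −0.87), SD (0.95, 1.02), correlation 0.28; worst miss 3.8 points.
- Two-component mixture: weight 0.31, mean (−1.24, −1.26), SD (0.52, 1.27), correlation 0.53; weight 0.69, mean (−1.29, −0.48), SD (1.40, 0.86), correlation 0.21; worst miss 1.4 points.

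The plan's own figures for 2/6 are 13.9% at 420 (scenario 9) and 16.4% at 630 (scenario 14). The fits give 13–14% and 16–17%.

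P(over) at an untested dose, range over the fits (420 after 0/3 at 280; 630 after 0/3 at 280 and 420):

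| Data in cohort | 280 | 420 | 630 |
|---|---|---|---|
| 2/3 | 44–48% | 30% | 36–37% |
| 2/4 | 35–36% | 23–24% | 28–29% |
| 2/5 | 27–28% | 17–19% | 21–22% |
| 2/6 | 20–21% | 13–14% | 16–17% |
| 3/6 | 44–45% | 32% | 36–37% |

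**3. How often the rule is silent.** The second DLT falls at patient 3 with probability 2p²(1−p), where p is the true DLT rate; the first-2 rule fires with probability p². At p = 1/3: 2 × 0.111 × 0.667 = 14.8%, against 11.1%. At p = 0.5: 2 × 0.25 × 0.5 = 25%, against 25%. This assumes each outcome is known before the next entry.

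**4. Effect of a pause at 2 of the first 3.** Take a six-patient cohort at an untested dose with one-at-a-time entry. The current rule stops at 2/2. The added rule also stops at 2/3, since P(over) is above 25% there at all three doses. Otherwise the cohort runs to six, and the dose fails at 3/6 or more.

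- Mean patients, current: 2p² + 6(1−p²).
- Mean patients, with the fix: 2p² + 3·2p²(1−p) + 6[1 − p² − 2p²(1−p)].
- Mean DLTs: p × mean patients.
- Dose fails, current: p² + P(at least 3 of 6) − p²[1 − (1−p)⁴].
- Added failures: those stopped at 2/3 that would have ended at 2/6, 2p²(1−p)⁴.

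| True rate | New pauses | Mean patients | Mean DLTs | Dose fails |
|---|---|---|---|---|
| 25% | 9.4% | 5.75 → 5.47 | 1.44 → 1.37 | 18.9% → 22.9% |
| 40% | 19.2% | 5.36 → 4.78 | 2.14 → 1.91 | 47.6% → 51.8% |
| 50% | 25.0% | 5.00 → 4.25 | 2.50 → 2.13 | 67.2% → 70.3% |

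For example, at 50%: 0.25 × 2 + 0.25 × 3 + 0.50 × 6 = 4.25 patients.

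**The case against.** **Other safeguards exist.** A reader might infer that the first-2 rule is the only written response of any kind. It is not. The affected patient's dosing is interrupted (6.3.1), SAEs reach the sponsor within 24 hours (8.2.2), the sponsor coordinates cohort assignment (6.5.2), and investigators must act for safety (12.1). The sponsor would usually know of the DLTs and could stop. This stands, but none of these provisions requires a pause or a model run.

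**Cohort size is not fixed in advance.** Nothing prevents the sponsor closing a cohort at three evaluable patients, so the exposure is permitted and not directed. This is fair, and it is why the point is a gap.

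**Entry may overlap.** The glossary describes a cohort as patients treated at the same time, and 4.1 foresees patients arriving when no slot is open. The savings above are therefore upper bounds, falling to zero if all six enter together.

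**The fix does not sharpen dose selection.** Rejection rises by 4.0 points at a true rate of 25% and by 3.1 points at 50%. This stands: the gain is fewer patients exposed. The plan keeps 420 and 630 after 2/6 (scenarios 9 and 14), so finishing a cohort after 2/3 can legitimately rescue an on-target dose.

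**The prior is unknown.** Every P(over) in Table 14-15 is 25% or less, so back-fitted values above that are extrapolations. Only the 280 result rests on print.

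**Conclusion.** The point holds for cohorts that enrol more than 3 patients at an untested dose, when 2 of the first 3 have a DLT and the second is at patient 3. The plan's scenarios step down on those data, but its enrolment text asks for nothing. At 280 mg/m² the 25% limit is exceeded on printed figures; at 420 and 630 P(over) is about 30% and 37%, conditional on the back-fit.

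Four wider readings are not supported:

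- **The plan contradicts its own overdose control.** That criterion is written for the next cohort, so this is an omission.
- **Any second DLT should stop the cohort.** At 2/4 and 2/5 several values lie within about 4 points of 25% and are not decisive. If the back-fit is taken at face value, stopping at any second DLT through patient 5 at 280 raises failure of an on-target 25% dose from 19% to 37%.
- **The same gap matters at a previously tested dose.** There, 2/3 in the new cohort passes after an earlier 0/3 (13–21%) and fails after an earlier 1/3 (30–46%), by back-fit.
- **Cohorts of 3 are affected.** They close and the model runs. Whether one may be enlarged is unclear: the glossary says "Cohorts are not expanded, new cohorts are enrolled", while the footnote to Table 6-1 says "Cohorts may be expanded at any dose level below MTD in order to better understand safety, PK or PD".

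The size is modest: at a true rate of 50%, at most about 0.4 DLTs saved per six-patient cohort. SAP 2.5 records that the MTD/RDE was already determined, so this is a point to consider about the rule as written and for any reuse of it.

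**What to change.** Add to Protocol 6.2.2: *if 2 of the first 3 patients in an incomplete cohort at a previously untested dose have a DLT, pause further enrolment to that cohort and re-run the BLRM with all data; resume only if the dose still meets the 25% overdose criterion and the dose-decision meeting agrees.* Keep the existing first-2 rule. For a second DLT at patient 4 or later, leave a re-run to the dose-decision meeting, because a hard stop there is a debatable trade-off.

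The cost is one sentence, occasional extra model runs and calls by existing staff, and a check of the operating characteristics with the rule included. At an on-target rate of 25%, about 9% of six-patient cohorts would pause newly, and the chance of the dose failing the overdose criterion rises from 19% to 23%. Overlapping entry shrinks both cost and benefit.

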6.2.2.1 Implementation of dose escalation decisions

To implement dose escalation decisions, the available toxicity information (including AEs and laboratory abnormalities that are not DLTs), the recommendations from the BLRM, and the available PK and PD information will all be evaluated by the Investigators and Novartis study personnel (including the study physician and statistician) during a dose decision meeting by teleconference. Drug administration at the next higher dose level may not proceed until the investigator receives written confirmation from Novartis indicating that the results of the previous dose level were evaluated and that it is permissible to proceed to a higher dose level.

Dose escalation will continue until MTD and/or the RDE is reached. The dose for the expansion part will either be the MTD, or a lower dose that is determined to be the RDE.

6.2.2.2 Intra-Patient dose escalation

The starting dose on this study is close to the predicted MTD and therefore, intra-patient dose escalation is not permitted at any time during this study.

6.2.3 Definitions of DLTs

A DLT is defined as an AE or clinically significant abnormal laboratory value assessed as unrelated to disease, disease progression, inter-current illness, or concomitant medications that occurs within the first 28 days of treatment with LEE011 and meets any of the criteria included in [Table 6-2](#). NCI CTCAE version 4.03 will be used for all grading. For the purpose of dose-escalation decisions, DLTs will be considered and included in the BLRM.

The investigator must notify the Sponsor immediately of any unexpected CTCAE grade ≥ 3 AEs or laboratory abnormalities. Prior to enrolling patients into a higher dose level, CTCAE grade ≥ 2 AEs will be reviewed for all patients at the current dose level.

[figure not shown]

Table 6-2 Criteria for defining dose-limiting toxicities

TOXICITY	DLT CRITERIA
Hematology	CTCAE grade 4 neutropenia lasting more than 7 consecutive days
	CTCAE grade 4 thrombocytopenia
	CTCAE grade 3 or 4 neutropenia with fever (temperature $\geq 38.5^{\circ}\text{C}$)
ECG QT Interval	QTc interval ≥ 501 ms on at least two separate ECGs
Gastro-intestinal	\geq CTCAE grade 3 nausea or vomiting despite optimal anti-emetic therapy \geq CTCAE grade 3 diarrhea despite optimal anti-diarrhea treatment
Hepato-biliary	\geq CTCAE grade 3 total bilirubin \geq CTCAE grade 3 ALT (isolated increases in AST without concomitant increases in ALT will not be considered dose-limiting, because of the non-specific nature of AST)
Non-hematologic events	\geq CTCAE grade 3, except for the exclusions noted below
Exceptions to DLT criteria	Grade 3 alopecia
	< 72 hours of CTCAE grade 3 fatigue
	Grade 3 fever or infection without neutropenia < 5 days duration
	Grade 3 laboratory abnormalities that are responsive to oral supplementation or deemed by the investigator to be clinically insignificant
CTCAE version 4.03 will be used for all grading. Optimal therapy for vomiting or diarrhea will be based in institutional guidelines, with consideration of the prohibited medications listed in this protocol.	

[figure not shown]

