6.4.1 Permitted concomitant therapy

Medications required to treat AEs, manage cancer symptoms, concurrent stable diseases and supportive care agents, such as packed red blood cells (PRBC)s, pain medications, anti-emetics and anti-diarrheals are allowed. Stable doses of steroids from study entry and oral contraceptive pills are permitted. The use of any other potential new concomitant medications may be discussed between the investigator and the sponsor on a case by case basis.

Transfusions or growth factor support for white cell counts, platelets or red blood cells are not permitted during Cycle 1, unless the patient has already experienced a DLT. Transfusions and growth factor support should not be used prophylactically during Cycle 1. Patients with bone marrow metastatic disease who are not evaluable for hematological toxicities are exempt.

The patient and/or patient's parent or guardian must be told to notify the investigational site about any new medications he/she takes after the start of the study drug. All medications (other than study drug) and significant non-drug therapies (including physical therapy and blood transfusions) administered during the study must be listed on the Concomitant Medications or Significant Non-Drug Therapies eCRF, respectively.

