6.4.2 Concomitant therapy requiring caution

The following therapies are permitted in this study, however they should be used with caution:

- Medications that are moderate inhibitors or inducers of CYP3A4/5. (Refer to [Appendix 6](#)).

- Sensitive substrates of CYP3A4/5 that do not have a narrow therapeutic index (Refer to [Appendix 6](#)).
- Known BSEP inhibitors listed in [Appendix 6](#).
- Agents that are metabolized predominantly by CYP1A2 with a narrow therapeutic index and agents that are strong inhibitors of CYP1A2 listed in [Appendix 6](#).
- Medications that carry a moderate-low risk for QT prolongation listed in [Appendix 6](#).

Patients receiving such medications must be carefully monitored for potentiation of toxicity due to any individual concomitant medication, and may require dose titration of the drug substance.

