
¹ Any drug mentioned in the above list should be contraindicated if they are excluded based on any other exclusion criteria as specified in Section 5.3 of the Study Protocol
 
² Sensitive substrates: Drugs whose plasma AUC values have been shown to increase 5-fold or higher when co-administered with a potent inhibitor.
 
This list of CYP substrates was compiled from the Indiana University School of Medicine's "Clinically Relevant" Table (http://medicine.iupui.edu/clinpharm/DDIs/ClinicalTable.aspx; accessed April 4th, 2012), from the FDA's "Drug Interaction Studies —Study Design, Data Analysis, Implications for Dosing, and Labeling Recommendations, DRAFT GUIDANCE, February 2012 (For further information, please see the FDA's website: http://www.fda.gov/downloads/Drugs/GuidanceComplianceRegulatoryInformation/Guidances/UCM292362.pdf (accessed April 04, 2012))", and from the University of Washington's Drug Interaction Database
	

BSEP transporter

In order to avoid clinically significant drug-drug interactions, the co-administration of known BSEP inhibitors causing further BSEP inhibition are to be used with caution ([Table 14-9](#)).

Table 14-9 BSEP transporter: List of medications causing inhibition to be used with caution

Drug Name	Drug Class
Bosentan	Antihypertensive
Cyclosporin A	Immunosuppressant
Fusidate	Antibiotic
Glibenclamide	Sulfonylurea
Lovastatin	Antihyperlipidemic
Nefazodone	Antidepressant
Rifampicin	Antitubercular
Ritonavir	Antiretroviral
Sulindac	Nonsteroidal anti-inflammatory
Troglitazone (TGZ-sulfate)	Anti-diabetic

QT prolongation

Due to the concern that LEE011 will cause QT prolongation, caution should be exercised with all medications that are known to produce this effect. Those known to have a strong signal will be prohibited ([Table 14-10](#)) and others are to be used with caution ([Table 14-11](#)).

[figure not shown]

Table 14-10 QT prolongation: List of excluded medications

Drug Name	Drug Class
Amitriptyline, Desipramine, Imipramine	Antidepressants
Chloroquine	Antimalarials
Chlorpromazine, Mesoridazine, Risperidone	Antipsychotics
Itraconazole, Ketoconazole	Antifungals
Tacrolimus, Arsenic trioxide, Domperidone	Miscellaneous drugs

Table 14-11 QT prolongation: List of medications to be used with caution

Drug Name	Drug Class
Dolasetron, Ondansetron, Tropisetron	Anti-emetics
Doxepin, Maprotiline, Venlafaxine,	Antidepressants
Gatifloxacin, Moxifloxacin, Sparfloxacin	Quinolone antibiotics
Halofantrine	Antimalarials

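### A Cycle 1 QTc event judged related to both LEE011 and a permitted QT-risk drug is, read literally, not a DLT under Protocol section 6.2.3

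*Protocol*

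**What the plan says.** Protocol section 6.2.3 defines a DLT as an adverse event or clinically significant laboratory abnormality "assessed as unrelated to disease, disease progression, inter-current illness, or concomitant medications that occurs within the first 28 days" of LEE011 treatment that meets a criterion in Table 6-2. One criterion is QTc of 501 ms or more "on at least two separate ECGs". Only events classed as DLTs enter the BLRM (6.2.3, 10.4.1).

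The protocol expects LEE011 itself to act on the QT interval. The drug lists in Appendix 6 are introduced with the words "Due to the concern that LEE011 will cause QT prolongation".

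Drugs with QT risk are nevertheless allowed on study. Section 6.4.1 states that "pain medications, anti-emetics and anti-diarrheals are allowed". Section 6.4.2 permits, with caution, "Medications that carry a moderate-low risk for QT prolongation listed in" Appendix 6. Table 14-11, the list in question, has an anti-emetic row: "Dolasetron, Ondansetron, Tropisetron". Neither section limits these drugs in Cycle 1 on QT grounds.

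Section 6.3.1 ties interruption to the DLT label: "If a patient experiences a DLT, then treatment with LEE011 must be interrupted". It gives no separate rule for QTc.

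**The concern.** The attribution test is framed around the other possible causes. An event must be assessed as unrelated to each of them, and a contribution from LEE011 does not rescue it. For most toxicities this may rarely matter. For QTc the protocol creates the overlap itself, because it expects the study drug to prolong QT and permits other drugs that do the same.

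Such co-medication is foreseeable. Nausea and vomiting are among the most frequent treatment-related events in the adult study (section 1.2.1.2). In Table 6-2 they are dose-limiting only at or above "CTCAE grade 3 nausea or vomiting despite optimal anti-emetic therapy". A child who vomits in Cycle 1 may well be given one of the anti-emetics in Table 14-11.

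At stake is the primary endpoint. With cohorts of 3 to 6 patients, a single event that is not counted can change the dose given to the next children, and the error runs in the unsafe direction.

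**Working it through.** The protocol states no figure for this point, so the check is mainly one of reading.

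**1. Does the definition exclude a jointly caused event?** An event assessed as related to both LEE011 and a concomitant drug is not assessed as unrelated to concomitant medications. It fails the test in 6.2.3 before Table 6-2 is reached. The general row in Table 6-2 for grade 3 or higher non-hematologic events sits under the same test and does not recover it.

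**2. What depends on the label?**
- the BLRM input and primary endpoint (6.2.3, 10.4.1)
- the rule that moves to a lower dose, or stops the cohort, when the first two patients have a DLT (6.2.2)
- mandatory interruption (6.3.1)

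**3. How does the patient then enter the model?** Under 10.1.3 a patient without a DLT enters the dose-determining set if at least 16 of 21 doses were taken and safety evaluation was sufficient; otherwise the patient is left out. Take 2 DLTs in 6 patients, one of them of this kind:
- as it should count: 2/6 = 33.3%
- kept as a non-DLT: 1/6 = 16.7%
- left out: 1/5 = 20%

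Both routes lower the observed rate.

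**4. What can one DLT fewer do?** These pairs in Table 14-15 differ by one DLT at the last dose tested:

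| Scenarios | Last dose (mg/m²) | DLTs | Next dose (mg/m²) | Ratio |
|---|---|---|---|---|
| 4 v 5 | 420 | 0/3 v 1/3 | 630 v 420 | 1.50 |
| 5 v 6 | 420 | 1/3 v 2/3 | 420 v 280 | 1.50 |
| 9 v 10 | 420 | 2/6 v 3/6 | 420 v 280 | 1.50 |
| 11 v 12 | 630 | 0/3 v 1/3 | 850 v 630 | 1.35 |
| 12 v 13 | 630 | 1/3 v 2/3 | 630 v 420 | 1.50 |
| 14 v 15 | 630 | 2/6 v 3/6 | 630 v 420 | 1.50 |

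The size of each step mostly reflects the grid: Appendix 7 picks next doses to match the provisional levels, which Table 6-1 spaces 50% apart. The table would look the same whichever DLT was lost. Nor does every DLT change the step: 1/6 at 280 mg/m² (scenario 7) leads to 420, as does 0/3 (scenario 1). The posteriors cannot be recomputed because the prior is redacted.

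**5. Can a frequency be given?** Section 1.2.1.2 reports 4 + 8 + 13 + 3 = 28 adults at 600 mg or above and one grade 3 QTc event: 1/28 = 3.6%, exact 95% CI 0.1% to 18.3%. Assume that grade 3 corresponds to 501 ms or more, that a share *f* of patients takes a Table 14-11 drug, and that the drug adds no risk. The chance of at least one such event in *n* patients is 1 − (1 − *f* × rate)^n.
- Rate 1/28, *n* = 6: 4.2% (*f* = 0.2) to 12.2% (*f* = 0.6)
- Rate 1/28, *n* = 12: 8.2% to 22.9%
- Confidence limits carried through: about 0.1% (*n* = 6, *f* = 0.2, lower limit) to about 75% (*n* = 12, *f* = 0.6, upper limit)

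The values of *f* are assumptions with no source in the documents, and the rate rests on one event. By dose it is 0/12 at 600 and 750 mg and 1/16 at 900 and 1200 mg. A range of 0.1% to 75% is no estimate.

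**The case against.** The strongest reply is that the definition calls for a judgment. That another drug is a plausible cause does not mean the event will be assessed as related to it. Investigators may read the clause as removing only events clearly due to something else. The adverse event form records relationship to study treatment only (8.1.1), so the documents do not show how a mixed case would be called. This stands. A reader might infer that every QTc event in a child taking a Table 14-11 drug drops out of the DLT count. The text does not support that. The problem arises when the event is judged related to both.

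Second, the event would not go unnoticed:
- Escalation decisions draw on all Cycle 1 toxicity of grade 2 or higher and on PK, and smaller dose increases are allowed (6.2.2).
- Events that are not DLTs are discussed at the dose meeting (6.2.2.1), and those of grade 2 or higher are reviewed before anyone enters a higher dose level (6.2.3).
- Patients on these drugs must be watched for increased toxicity (6.4.2).
- QTc of 501 ms or more prompts a PK sample, abnormal ECGs are repeated after electrolyte correction, and all ECGs are read centrally (7.2.2.5.5).
- QTc categories are tabulated (10.5.2.4).

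All of this is real, but none of it returns the event to the DLT count. Section 10.1.3 requires sponsor and investigators to be able to conclude that no DLT occurred, but that conclusion rests on the same definition.

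Third, exclusion 13 bars patients taking QT-prolonging drugs, and a footnote to Table 14-7, which lists ondansetron, contraindicates any listed drug that section 5.3 excludes. But exclusion 13 concerns drugs in use at entry, while 6.4.2 and Table 14-11 permit these drugs on study. The documents leave that tension unresolved. Dolasetron and tropisetron are not in Table 14-7.

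Finally, counting jointly caused events as DLTs pulls the estimated MTD downward. That is a fair cost, taken up under the fix.

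**Conclusion.** The point holds as a defect in the definition. Read literally, section 6.2.3 removes from the DLT count a Cycle 1 QTc event judged related to both LEE011 and a permitted QT-risk drug. The observed DLT rate is then too low for a toxicity the protocol expects, and the BLRM, the first-two-patients rule and the mandatory interruption do not see the event.

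Its size cannot be stated as a frequency. A reader might also take the 35% to 50% dose differences in Table 14-15 as the effect of this clause. They are not: they show only that one DLT fewer of any kind can move the next dose up one step of the grid.

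The conclusion assumes that sites apply the clause as worded. If they read it as covering only clear alternative causes, the count is right, but the protocol does not tell them to, and two sites could classify the same event differently.

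The SAP for the final report (section 2.5) states that the MTD/RDE was determined before enrollment was halted, and plans no further MTD analysis. What remains for this trial is therefore mainly to check whether any event was excluded on this ground.

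**What to change.** Add to section 6.2.3: QTc of 501 ms or more on at least two separate ECGs in Cycle 1 is a DLT if there is a reasonable possibility that it is related to LEE011, even if a concomitant drug may have contributed; it is excluded only when clearly and solely due to another cause. The same wording could sensibly apply to the other Table 6-2 criteria, which sit under the same clause.

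Enter such events in the BLRM as DLTs, and re-run it without them as a sensitivity analysis for the dose meeting. With dose finding already closed, apply the rule retrospectively: look for Cycle 1 events that met the QTc criterion but were excluded because of a concomitant drug, and re-run the model if any are found.

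The cost is two sentences and one extra model run when such an event occurs. No new data are needed, since relationship to LEE011 (8.1.1) and all concomitant drugs (6.4.1) are already recorded. The downside is slightly more cautious escalation, and a required interruption, when the other drug was the main cause. The sensitivity run shows how far the dose recommendation depends on that choice.
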